In all of the published literature, the overall incidence of TdP associated with ibutilide is 2.0%. TdP has never been reported at the dose that we propose to administer in this study. The lowest dose of ibutilide that has ever been associated with TdP in the published literature is 0.5 mg, and there has only been one reported case at this dose. That is more than double the dose that we propose to administer. In order to achieve this dose in our study, a patient would have to weight 166 kg (based on our dose of 0.003 mg/kg). No subject in this study will receive a dose as high as 0.5 mg, because we have an upper weight exclusion of 135 kg. Therefore, this risk of TdP in our volunteer subjects, at a low dose of 0.003 mg/kg (roughly 20% of the lowest clinical dose), is extremely low, and again, TdP has never been reported at this low dose.

Oral progesterone 400 mg once daily is the dose that was effective for attenuating drug-associated QTcI interval response in premenopausal women. Oral progesterone 400 mg daily has been administered to pre-menopausal women with minimal adverse events including abdominal cramping, nausea, vomiting, mood disturbances and menstrual spotting or bleeding following withdrawal of the medication. Subjects will be monitored via phone calls throughout the dosing period and advised to discontinue the medication if adverse events become intolerable.

Risks related to the blood draws and intravenous catheter placement will be minimized through the use of experienced staff placing the intravenous catheter. Subjects will be evaluated for anemia prior to inclusion in order to minimize the risk of anemia due to blood draws.

Safety Monitoring

Any serious or unexpected adverse event will be reported to the Research and Sponsored Programs Committee on the IUPUI campus within 3 working days of notification of the event. A written report of the adverse event will also be submitted. Any Serious Adverse Event (SAE) that is observed during the study or within 30 days after administration of ibutilide will be recorded and reported to the SAE contact investigator. The SAE contact investigator will serve as the chair for the Data and Safety Monitoring Board (DSMB).

A Data Safety & Monitoring Board (DSMB) has been established for this study. The DSMB will be chaired by [name], PhD, Assistant Professor of Obstetrics & Gynecology, School of Medicine, Indiana University. The other members of the DSMB are:

- [name], Assistant Professor, College of Pharmacy, Purdue University, and Faculty Associate, Center on Aging and Life Course. [name] has substantial experience in clinical research studies, and was recently awarded an NIH R01 as principal investigator for a large clinical investigation
- [name], Associate Professor, College of Pharmacy and Health Sciences, Butler University. [name] previously was Associate Director of the Center for Medication Safety Advancement at Purdue University, and has extensive experience in assessing patient safety.

. The designated DSMB will be responsible for notifying the Sponsored Programs Committee in the time specific time allotted from above.

Study/Data Monitoring

The following documents will be on file in the primary investigators office before patient enrollment:

Copy of the IU IRB/Ethics Committee approval of the protocol and consent;
Copy of the IRB approved informed consent;

A pre-study start meeting will take place to ensure that investigators and other essential personnel are aware of the protocol requirements for ibutilide administration and data collection.

The DSMB will meet after 1/4 (n=10) of the study subjects have completed the study, after 1/2 of the study subjects have completed the study (n=20), and after 3/4 (n=30) of the study subjects have completed the study. The DSMB will monitor subject recruitment, accrual, retention, adverse event data, results of related studies that may impact subject safety, and procedures designed to protect the privacy of subjects. The DSMB will analyze and interpret data submitted by the principal investigator. In the unlikely event that a subject experiences an ibutilide-associated arrhythmia, the DSMB will determine whether the study should continue or should be suspended.

Data from the study will be monitored continuously throughout the study and will be reviewed at each DSMB meeting.

Definitions (ICH Guideline on Clinical Safety Data Management: Definitions and Standards for Expedited Reporting and FDA Regulation 21 CFR 312.32, Final Rule October 7,1997)

- **Adverse Event:** Any untoward event, which occurs regardless of its causality, including and side effect, injury, toxicity or sensitivity reaction during testing of protocol treatments (whether or not considered drug-related), will be designated as an adverse clinical event.
- **Serious Adverse Event:** An event that is fatal, life-threatening, or leads to persistent or significant disability; one that requires or prolongs hospitalization; or one that results in a congenital anomaly, or significant medical event.
- **Unexpected Adverse Event:** Any adverse event not identified in nature, severity, or frequency in current package label for ibutilide or product information.
- Adverse events will be defined as any unfavorable and unintended sign (including an abnormal laboratory finding), symptom, or disease temporally associated with the use of a medical treatment or procedure that may or may not be considered related to the medical treatment or procedure. (NCI definition). The level of severity of an adverse event will be based on a grading scale which is adopted from the NCI Common Terminology Criteria for Adverse Events: Grade 1, Mild AE; Grade 2, Moderate AE; Grade 3, Severe AE; Grade 4, Life threatening or disabling AE; Grade 5, death related to AE. For prolonged QTc interval Grade 1, QTc>0.48-0.50 seconds; Grade 2, QTc >0.50 seconds and/or increase in QTc \geq 0.06 seconds above baseline; Grade 3, QTc >0.55 seconds; Grade 4, QTc >0.60 seconds and/or life-threatening signs or symptoms (e.g., arrhythmia, CHF, hypotension, shock, syncope) and/or *torsades de pointes*; Grade 5, Death.

Ethical Aspects of the Proposed Research

The minimum possible number of subjects is proposed, based on sample size calculations. Progesterone 400 mg orally daily was associated with no reported adverse effects.¹⁸ In our study,¹⁰ adverse effects associated with progesterone were primarily fatigue/malaise. Therefore, risks associated with oral progesterone appear minimal. Subjects will be carefully screened and a thorough physical examination will be performed prior to initiation of the protocol. Extensive exclusion criteria have been included to minimize the risk of adverse effects to subjects enrolled in the study.

Safety measures have been put into place to minimize the potential risks in this study, and the results of this study may provide benefit to society by enhancing patient safety.

DSMB Safety Monitoring

A Data Safety & Monitoring Committee (DSMB) has been established for this study. The DSMB will monitor subject recruitment, accrual, retention, adverse event data, results of related studies that may impact subject safety, and procedures designed to protect the privacy of subjects. The DSMB will analyze and interpret data submitted by

the principal investigator. In the unlikely event that a subject experiences an ibutilide-associated arrhythmia, the DSMB will determine whether the study should continue or should be suspended. During the anticipated two and a half-year duration of the study, the DSMB will meet after 1/4 (n=10) of the study subjects have completed the study, after 1/2 of the study subjects have completed the study (n=20), and after 3/4 (n=30) of the study subjects have completed the study.

The IRB will receive information regarding frequency and dates of monitoring, summary of cumulative adverse events, assessment of external factors, including scientific reports, therapeutic developments, & results of related studies that could impact subject safety, summaries of subject privacy and research data confidentiality outcomes, and any changes to the risk: benefit ratio.

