Subjects will be asked to come to the ICRC at IU Health University Hospital. An investigator will review the procedures and risks of the study in detail and obtain written informed consent. After written informed consent is obtained, subjects will undergo a screening history and physical examination performed by an investigator. Three 12-lead ECGs one minute apart (QTc will be averaged across ECGs to determine eligibility), height, weight and blood work will be obtained at this time to determine serum potassium, magnesium, liver enzymes, hematocrit. Premenopausal women will undergo a urine human chorionic gonadotropin (HCG) test to rule out pregnancy.

Once laboratory results are obtained and the physical is completed and the subject has met inclusion criteria and has no exclusion criteria, the subject will be enrolled in the study. If the subject meets any exclusion criteria, they will not be allowed to proceed in the study. This process will take approximately 1 hour.

Immediately following the screening history and physical examination, subjects will be randomly assigned to two groups:

Group A: (n= 20 subjects)

Each subject will take two placebo capsules once daily in the evening for 7 days.

Group B: (n= 20 subjects)

Each subject will take oral progesterone 400 mg orally once daily (two x 200 mg capsules) in the evening for 7 days.

Subjects will be sent home with one week's supply of the study medication to which they are initially randomized and a medication diary with which to keep track of when they take the medication, any adverse effects they may experience, and any changes in their own

concurrent medications. They will receive written and verbal instructions about the study medication and dates will be established for Visit 2.

Visit 2:

Prior to the visit subjects will be NPO and remain NPO until 4 hours after the end of the ibutilide dosing. Subjects may drink non-caloric drinks during this period such as coffee, tea, diet soda, water ect. If the serum potassium concentration is low as defined previously in the protocol, then the subject may have orange juice or a banana as previously defined in the protocol.^{26,27,28}

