Continuous ECG monitoring will be initiated prior to ibutilide administration and will continue until the post-ibutilide Bazett's-corrected QT interval is < 450 ms, which generally occurs within 2 hours following administration of this low, subtherapeutic dose of ibutilide. Three 12 lead ECGs approximately one minute apart (three ECGs within a total of 5 minutes) will be selected for QT interval measurement before ibutilide administration and after ibutilide at: at 5 minutes during infusion, end of infusion, 5, 10, 15, 20, 30 and 45 minutes and 1, 2, 4, 6, and 8 hours. Blood (6 mL) for determination of ibutilide concentrations will be obtained from the indwelling catheter in the arm contralateral to that into which ibutilide was infused at approximately the following times (within 5 minutes of the times listed) 5 minutes during infusion, the end of infusion, and 5, 10, 15, 20, 30 & 45 minutes, and 1, 2, 4, 6, and 8 hours following end of infusion. An 8-hour data

collection and monitoring period is sufficient, as QT_c intervals return to baseline within 2-6 hours.^{9,10}

At the end of this visit, and after a minimum 14-day washout period, subjects will take another of the study drugs as follows:

Group A: (n= 20 subjects)

Each subject will take oral progesterone 400 mg orally once daily (two x 200 mg capsules) in the evening for 7 days.

Group B: (n= 20 subjects)

Each subject will take two placebo capsules once daily in the evening for 7 days.

Subjects will be sent home with one week's supply of the study medication to which they are randomized for this phase and a medication diary with which to keep track of when they take the medication, any adverse effects they may experience, and any changes in their own concurrent medications. They will receive written and verbal instructions about the study medication and dates will be established for Visit 3.

At 3-7 days following the study visit, subjects will be called/texted or emailed based on preference to assess for any potential adverse events related to study medications or procedures.

Visit 3:

Prior to the visit subjects will be NPO and remain NPO until 4 hours after the end of the ibutilide dosing. Subjects may drink non-caloric drinks during this period such as coffee, tea, diet soda, water etc. If the serum potassium concentration is low as defined previously in the protocol, then the subject may have orange juice or a banana as previously defined in the protocol.^{26,27,28}

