Continuous ECG monitoring will be initiated 30 minutes prior to ibutilide and will continue until the post-ibutilide Bazett's-corrected QT interval is < 450 ms, which generally occurs within 2 hours following administration of this low, subtherapeutic dose of ibutilide. Three 12 lead ECGs approximately one minute apart (three ECGs within a total of 5 minutes) will be selected for QT interval measurement before (time 0) and after ibutilide at: at 5 minutes during infusion, end of infusion, 5, 10, 15, 20, 30 and 45 minutes and 1, 2, 4, 6, and 8 hours. Blood (6 mL) for determination of ibutilide concentrations will be obtained from the indwelling catheter in the arm contralateral to that into which ibutilide infused was approximately the following times (within 5 minutes of the times listed) 5 minutes during infusion, at the end of infusion, and 5, 10, 15, 20, 30 & 45 minutes, and 1, 2, 4, 6, and 8 hours following end of infusion. An 8-hour data collection and monitoring period is sufficient, as QT_c intervals return to baseline within 2-6 hours.^{9,10}

In addition, blood will be drawn to determine serum progesterone, estradiol, and potassium concentrations at the same time as the time 0 ibutilide concentration is drawn. If the subjects is found to have hypokalemia as defined in the exclusion criteria, then they will be withdrawn from the study.

At 3-7 days following the study visit, subjects will be called/texted or emailed based on preference to assess for any potential adverse events related to study medications or procedures.

Following visit 3, subjects' participation in the study will be complete.

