8.0 Statistical Considerations

Statistical analysis will be performed separately for the two subject populations:

- Postmenopausal women (progesterone vs placebo)
- Premenopausal women (progesterone vs placebo)

QT intervals will be corrected for heart rate using two correction methods, the Fridericia (QT_F) and Framingham (QT_{Fra}) methods.

Study Endpoints: Comparison of progesterone and placebo phases for: 1) Baseline (pre-ibutilide) maximum QT_F & QT_{Fra} 2) Ibutilide effect on maximum QT_F & QT_{Fra}, 3) Ibutilide effect on maximum % change in QT_F & QT_{Fra}, and 4) Ibutilide effect on AUEC_{0-1.17} and AUEC_{0-8.17}. Endpoints will be correlated with progesterone concentrations. 5)

Statistical analyses: Means (standard deviations) or medians (interquartile range) will be presented for continuous variables. Distribution normality will be assessed using the Kolmogorov-Smirnov test. Paired t-test (if normality holds) or signed-rank test (if normality does not hold) will be used to compare outcome measures between the two treatment phases; 95% confidence intervals will be calculated. SAS 9.4 (Cary, NC) will be

used. Correlations between the primary endpoints and serum progesterone concentrations will be performed using Pearson's correlation coefficient.

Anticipated Outcomes: During the progesterone phase, the following outcome measures will be significantly lower than vs placebo: 1) Pre-ibutilide QT_F and QT_{Fra}; 2) Post-ibutilide maximum QT_F and QT_{Fra}; 3) AUEC 1 hour and 8 hours after ibutilide; 4) Post-ibutilide % change in maximum QT_F and QT_{Fra}, 5) J-T_{peak} and T_{peak-T_{end}}.

Sample Size Calculation: In this 2-way crossover study, at a two-sided α level of 0.05 and a power of 0.80, a sample size of 20 subjects in the postmenopausal population and n=20 subjects in the premenopausal population will be sufficient to detect a difference in maximum QT_F and QT_{Fra} of 15 ms, assuming a QT_F and QT_{Fra} interval prolongation of 24±12 ms associated with ibutilide in the absence of progesterone.

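### The pre-dose ECG is specified differently at the two visits of a paired comparison and rests on a single time point; one common, averaged baseline would gain precision at low cost.

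*Combined protocol and SAP*

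**What the plan says.** Section 5.0 describes the two treatment visits separately.

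- **Visit 2.** "Continuous ECG monitoring will be initiated prior to ibutilide administration", with no lead time. The triplicate "will be selected for QT interval measurement before ibutilide administration and after ibutilide at: at 5 minutes during infusion" and so on; the pre-dose reading has no clock time.
- **Visit 3.** "Continuous ECG monitoring will be initiated 30 minutes prior to ibutilide". The triplicate "will be selected for QT interval measurement before (time 0) and after ibutilide at" the same list of later times, so the pre-dose reading is labelled time 0.
- **Both visits.** The replicate rule is identical: "Three 12 lead ECGs approximately one minute apart (three ECGs within a total of 5 minutes) will be selected for QT interval measurement". There is one pre-dose time point and 13 later ones (2 tied to the infusion, 6 from 5 to 45 minutes, 5 from 1 to 8 hours). No rest period or body position is given.

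The order of progesterone and placebo is randomized. Averaging of triplicates is stated only for screening: "QTc will be averaged across ECGs to determine eligibility".

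In section 8.0, endpoint 1 is the pre-ibutilide QTc, worded as a *maximum*, and endpoint 3 is the maximum % change. Maximum QTc and the AUEC endpoints are not described as baseline-subtracted. The comparison is a paired t-test or signed-rank test with no period term.

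**The concern.** Each woman's two visits form one paired difference, so the pre-dose measurement should follow one rule. As written, the Visit 2 triplicate could be taken soon after the leads are attached or just before dosing, while at Visit 3 it is tied to time 0. Cannula placement, blood draws and, if potassium is low, juice or a banana all come before dosing. The plan otherwise keeps the women fasting and cites work on QT shortening after food, so where the reading falls in that sequence could matter.

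The single time point is a separate matter. Three ECGs within 5 minutes reduce reading error but cannot average out slower variation. Whatever error remains enters endpoint 1 in full and enters endpoint 3 through its denominator. At stake is the width of the intervals for those two endpoints, and whether the same quantity is measured at both visits.

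**Working it through.** **The plan's own sample size.** Inputs from section 8.0: difference 15 ms, SD 12 ms, two-sided α 0.05, power 0.80, n=20 per population. A parallel-group normal approximation needs 11 per arm, 22 in total; 10 per arm gives power 0.798. That is the route by which 20 is approximately reproduced.

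The planned test is paired. If 12 ms is the SD at each visit:

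- within-woman correlation 0.5: SD of the difference is 12; 8 women suffice; power at n=20 is above 0.999
- correlation 0: SD of the difference is 12√2 = 16.97; 13 women suffice; power at n=20 is 0.963

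At n=20, power for 15 ms stays at 0.80 until the SD of the difference reaches about 22.7 ms.

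**A visit offset, if there were one.** Assume 5 ms; the documents give no figure. With a 10/10 order split the bias in the treatment contrast is 0. With 8/12 it is 5 × (8 − 12)/20 = −1.0 ms. With no period term, a balanced split also adds 5 ms in quadrature to the SD of the difference: √(144 + 25) = 13.0, or √(288 + 25) = 17.7.

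**Gain from three pre-dose times.** None of these inputs is in the documents. Assumed: error SD of a triplicate mean s = 4 to 8 ms; within-woman between-visit SD τ = 0 to 8 ms; correlation r = 0 to 0.5 between pre-dose time points; baseline and post-dose errors independent.

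Var(paired change) = 2(s² + b² + τ²), with b² = s² for one time point and b² = s²(1 + 2r)/3 for three. For endpoint 1, Var(paired difference) = 2(b² + τ²).

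| Assumed s, τ, r | SD of paired change, 1 → 3 times | SD for endpoint 1, 1 → 3 times |
|---|---|---|
| 6, 0, 0 | 12.0 → 9.8 (−18%) | 8.49 → 4.90 (−42%) |
| 4, 8, 0.5 | 13.86 → 13.47 (−3%) | 12.65 → 12.22 (−3%) |

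The variance ratios for the change, 1.50 and 1.06, correspond to 50% and 6% more women.

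A second route starts from a given SD of the baseline-subtracted difference and removes 2s²(1 − 1/3), where s is now the SD between time points within a visit. At n=20 and s = 3 to 8 ms, the 95% half-width falls from 7.94 to between 7.78 and 6.66 ms (starting SD 16.97), or from 5.62 to between 5.38 and 3.58 ms (starting SD 12).

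**When the gain for a change vanishes.** Let the error be pure drift with correlation 0.5 per 15 minutes and the post-dose reading 15 minutes after time 0. In units of s²:

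- time 0 alone: 1 + 1 − 2(0.5) = 1.00
- mean of −30, −15 and 0: 1 + 0.611 − 2(0.5 + 0.25 + 0.125)/3 = 1.03

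Now let a fraction f of the error variance be independent reading error. One time point gives 1.00(1 − f) + 2f; three give 1.028(1 − f) + (4/3)f. They are equal at f = 0.028/(0.028 + 0.667) = 4%.

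If the post-dose reading comes only 5 minutes after time 0, the two drift terms become 0.413 and 0.685, and break-even is 0.272/(0.272 + 0.667) = 29%. So three times help the change once independent error is about 30% or more of the error variance, and sometimes well below that. For endpoint 1 the drift variance falls from 1 to 0.611 in both cases.

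**The case against.** The strongest reply is that the 30 minutes at Visit 3 is when monitoring starts, not the baseline window. The ECGs actually read follow the same triplicate rule at both visits, and the Visit 2 text is compatible with a 30-minute lead. A near-dose triplicate is a legitimate baseline, and the stated power is ample. All of this stands.

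It also disposes of several stronger readings that a reader might infer:

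- *That baseline truly differs by visit, or that the treatment contrast is biased.* Only the specification differs. No offset is documented, and randomized order would turn one mainly into variance.
- *That every endpoint suffers.* Only endpoints 1 and 3 are shown to depend on the pre-dose reading.
- *That the trial is underpowered for this reason.* It is not, under the inputs examined.
- *That 30 minutes of analysable 12-lead ECG is already recorded and ignored.* Section 6.0 speaks of telemetry, and section 9.0 describes ECGs on paper in one place and digitally in another, so this cannot be established.

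It is also fair that the variance formula treats the post-dose value as one reading, whereas endpoint 3 is a maximum over 13 times, and that 3% is not a floor, as the drift case shows. That no-gain case, however, needs almost no independent reading error. Nor does the reply answer the missing clock anchor for the Visit 2 triplicate.

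**Conclusion.** The point holds as one of consistency and precision. The pre-dose ECG has no lead time or anchor at Visit 2 and has both at Visit 3, and a single pre-dose time point carries endpoint 1 and the denominator of endpoint 3. Neither fact shows bias or endangers the stated power.

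Three averaged pre-dose times would lower the SD of the paired change by about 3% to 18% if baseline and post-dose errors are independent and the assumed SDs are about right. With almost pure slow drift the gain for endpoint 3 could be nil. Endpoint 1 gains unless the three readings are perfectly correlated; over the two cases tabulated, its SD falls by 3% to 42%. Aligning the wording rests on none of these assumptions. By itself it supplies missing detail; the averaging is the substantive improvement.

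**What to change.** In section 5.0, use the Visit 3 text for both visits: recording from 30 minutes before ibutilide, with the same rest and position, after cannula placement. Read triplicates at three fixed pre-dose times, for example −30, −15 and 0 minutes. Section 5.0 (Visit 3) ties the hormone and potassium draw to the time 0 ibutilide sample, so take the time 0 triplicate just before that draw, and state how close to the infusion it falls.

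In section 8.0, define baseline as the mean of all these readings, use it as the denominator of the % change, and reword endpoint 1 from a *maximum* to this mean. That changes the definition of endpoint 1 and should be recorded as such.

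Cost: 16 × 3 = 48 ECGs per visit instead of 14 × 3 = 42. That is six more per visit, or 480 over 80 visits (40 women, two visits each). If ECGs are taken on paper, the extra ones must be recorded as well as read, so the two descriptions of ECG capture in section 9.0 should be reconciled first. No extra visit, drug or blood sample is needed.

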3.0 Inclusion/Exclusion Criteria

Inclusion Criteria:

Specific Aims 1&2: Postmenopausal women, based on the following criteria:

- Age \geq 50 years **AND**
- No menstrual periods for \geq 365 days

Specific Aims 3&4: Premenopausal women, 21-40 years of age

Exclusion Criteria (apply to all specific aims):

- History of breast, uterine or ovarian cancer
- History of hysterectomy and/or ovariectomy
- Weight $>$ 135 kg
- Serum K^+ $<$ 3.6 mEq/L;
- Serum Mg^{2+} $<$ 1.8 mg/dL;
- Hematocrit $<$ 26%;
- Hepatic transaminases $>$ 3x upper limit of normal;
- Baseline Bazett's-corrected QT interval $>$ 450 ms
- Taking hormone replacement therapy
- Diagnosis of heart failure
- Symptoms associated with heart failure:
 - Pitting edema $>$ 2+
 - Crackles or rales on lung auscultation
 - S3 or S4 heart sounds
 - Unable to climb \geq 2 flights of stairs without becoming short of breath
- Current ECG rhythm of atrial fibrillation or other tachyarrhythmia

- Family or personal history of long-QT syndrome or sudden cardiac death not associated with acute myocardial infarction
- Concomitant use of any QTc interval-prolonging drug.
- Permanently paced ventricular rhythm
- Pregnancy
- Using any hormonal contraceptives (oral contraceptives, hormone-secreting intrauterine devices (IUDs), hormonal implants)
- Peanut allergy
- We will exclude subjects who are currently taking medications that induce or are moderate or strong inhibitors CYP 2B6/3A4/3A5 metabolism :

Carbamazepine (tegretol)	Phenytoin	Phenobarbital	Plioglitazone (actos)	Refabutin
Rifampin	St Johns Wort	Troglitazone (rezulin)		

Clopidogrel (Plavix)	Ticlopidine	Voriconazole	HIV antiviral meds	Verapamil
Diltiazem	Suboxone	Aprepitant		

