The risks associated with this investigation will be minimized by the administration of a subtherapeutic dose of ibutilide (0.003 mg/kg, approximately 20% of the lowest therapeutic dose, approximately 10% of the highest therapeutic dose). In addition, risks will be minimized, in large part, by the exclusion criteria employed, which will allow us to exclude patients that are at risk for experiencing excessive QT interval prolongation associated with a subtherapeutic dose of ibutilide. Subjects with specific risk factors for TdP will be excluded – these risk factors include hypokalemia, hypomagnesemia, pretreatment QTc interval > 450 ms, liver disease, NYHA class IV HF, LVEF < 20%, history of TdP, and taking other QT interval-prolonging drugs. During the day on which ibutilide will be administered, patients will be maintained on continuous ECG telemetry monitors until the post-ibutilide Bazett's-corrected QT interval is < 450 ms, which generally occurs within 2 hours following administration of this low, subtherapeutic dose of ibutilide. Ibutilide will be administered in the ICRC which is housed within University Hospital and has full medical services if needed in the case of an emergency. There is a cardiac arrest (code) cart in the CRC that includes magnesium sulfate. A physician investigator (or his designee) will be notified regarding the planned time of administration of ibutilide administration. Subjects will not be discharged from the ICRC if they have a QTc interval of > 450ms after treatment. They will be monitored until the QTc interval is below 450ms. This study has a DSMB to periodically monitor the safety and any adverse events which may occur.

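### Continuous ECG monitoring after ibutilide may stop once Bazett QTc is below 450 ms, with no minimum time; a 6-hour floor is a cheap safety improvement (minor)

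*Combined protocol and SAP*

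**What the plan says.** **Stop rule.** In 5.0 Study Procedures, under both Visit 2 and Visit 3, continuous ECG monitoring starts before ibutilide and "will continue until the post-ibutilide Bazett's-corrected QT interval is < 450 ms, which generally occurs within 2 hours following administration". Section 6.0 (Reporting of Adverse Events) gives the same rule for the dosing day: "patients will be maintained on continuous ECG telemetry monitors until the post-ibutilide Bazett's-corrected QT interval is < 450 ms". None of the three places sets a minimum duration, asks for a repeat reading or refers to the woman's own baseline.

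**Entry and discharge limits.** Section 3.0 lists as an exclusion "Baseline Bazett's-corrected QT interval $>$ 450 ms". Section 6.0 uses the same figure for leaving the unit: "Subjects will not be discharged from the ICRC if they have a QTc interval of > 450ms after treatment".

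**Duration of effect and observation period.** The paragraphs in 5.0 that hold the stop rule also say: "An 8-hour data collection and monitoring period is sufficient, as QT_c intervals return to baseline within 2-6 hours". Section 6.0 repeats the 2 to 6 hour range. Under Visit 2, sets of three 12-lead ECGs "will be selected for QT interval measurement before ibutilide administration and after ibutilide", the last of them at 8 hours. Visit 3 has the same schedule.

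**Recording method.** Section 9.0 describes a standard machine with paper output in one place and digital recordings in another.

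**The concern.** A threshold shows that a drug effect has resolved only if the measurement first rises above it. Here the stop value is practically the value every woman had to satisfy to be enrolled. The rule therefore cannot separate three states: an effect that has come and gone, one still rising, and one that never reached 450 ms. A woman in the third state meets the rule as soon as a post-ibutilide QTc is read. The remark about 2 hours describes what usually happens and is not a floor.

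What is at stake is live rhythm surveillance. Scheduled 12-lead ECGs sample the QT interval at fixed times. An arrhythmia between those times is picked up promptly by continuous monitoring. Followed as written, the rule lets that monitoring end before the plan's own return-to-baseline window has passed. No efficacy endpoint depends on it.

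**Working it through.** The plan derives no figure for this rule, so there is nothing to reproduce. The check compares the texts and adds one illustration.

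**1. The thresholds side by side**

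| Rule | Condition | Minimum time |
|---|---|---|
| Entry (3.0) | excluded if Bazett QTc > 450 ms | not applicable |
| Stop continuous monitoring (5.0, 6.0) | Bazett QTc < 450 ms | none |
| Discharge (6.0) | not while QTc > 450 ms | none |

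The entry and stop values differ only at exactly 450 ms.

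**2. Can a woman stay below 450 ms throughout? (illustration only)**

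Inputs: the sample size paragraph in 8.0 assumes that ibutilide without progesterone lengthens QTc by 24 ± 12 ms. That is a Fridericia/Framingham figure, applied here to Bazett by assumption. The documents give no baseline values, so those below are assumed. The mean rise m is varied from 20 to 30 ms to show sensitivity.

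Formula: P(peak < 450) = Φ((450 − baseline − m) / 12).

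| Assumed baseline | m = 20 | m = 24 | m = 30 |
|---|---|---|---|
| 410 ms | Φ(1.67) = 95% | Φ(1.33) = 91% | Φ(0.83) = 80% |
| 440 ms | Φ(−0.83) = 20% | Φ(−1.17) = 12% | Φ(−1.67) = 5% |

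The baseline at which staying below 450 ms is as likely as not is 450 − m: 430, 426 and 420 ms for m = 20, 24 and 30. So some eligible women can plausibly meet the stop rule even at peak effect. How many depends on a baseline distribution that the documents do not give.

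**3. What the scheduled ECGs cover**

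Times in minutes from the end of infusion (the infusion lasts 10 minutes): −5, 0, 5, 10, 15, 20, 30, 45, 60, 120, 240, 360, 480.

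- From −5 to 60 minutes there are nine sets, with gaps of 5, 5, 5, 5, 5, 10, 15 and 15 minutes.
- From 60 to 120 minutes there is one gap of 60 minutes.
- From 120 to 480 minutes there are three gaps of 120 minutes.

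The first hour is densely sampled. Any lapse in live surveillance matters from hour 1 onward, and the plan's 2 to 6 hour window has sets only at 2, 4 and 6 hours.

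**4. The two monitoring statements in the same paragraph**

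One sentence ends continuous monitoring on QTc alone. A later one calls an 8-hour period of data collection and monitoring sufficient. The second does not say that the monitoring is continuous, and it does not amend the first. Section 6.0 repeats only the first. Read literally, live monitoring may stop early while data collection runs to 8 hours.

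**The case against.** The strongest reply is that the context implies longer surveillance. Selecting ECGs at 2, 4, 6 and 8 hours suggests choosing from an ongoing recording, and the 8-hour period is justified by the very window said to be uncovered. That reading is reasonable, and it may be what the sponsor intends. But a recording kept for later selection is not the same as live watching, and the stop sentence is explicit and stated three times. The reply reduces the point to wording if 8 hours is the intention; it does not make the wording right.

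Second, an absolute threshold is a legitimate choice. Women who stay below 450 ms are within the limit accepted for entry and discharge, and 30 ms below the 480 ms at which the protocol's QTc adverse-event grading starts. The grading also counts a rise of at least 60 ms. Under the 24 ± 12 ms model that is three standard deviations above the mean, with probability about 0.13%. This stands: the group that meets the rule at once is not shown to be at raised risk.

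Third, the safeguards are substantial. Women stay about 10 hours in a hospital unit, a physician is told when ibutilide is due, and "There is a cardiac arrest (code) cart in the CRC that includes magnesium sulfate". On oversight, "In the unlikely event that a subject experiences an ibutilide-associated arrhythmia, the DSMB will determine whether the study should continue or should be suspended". The Appendix reports no torsades in 151 administrations at this dose, and no ventricular tachyarrhythmia in the investigators' own 118. The two instances above 500 ms among those 118 subsided quickly. This also stands, with one reservation: no row of the Appendix table at this dose identifies postmenopausal women, who are half of this trial.

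Fourth, a 6-hour floor is a judgement. It takes the upper end of the plan's range for every woman, and other remedies, such as 8 hours, would also serve.

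**Conclusion.** The point holds as a minor, safety-only improvement. The stop rule has no minimum time and uses essentially the entry limit, so it can be met immediately after dosing by women whose QTc stays below 450 ms, before the effect has resolved on the plan's own 2 to 6 hour estimate. The exposed period is live rhythm surveillance between scheduled ECGs after hour 1, and only if monitoring has in fact stopped and no live recording is running. The documents leave that open.

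A reader might infer three stronger things that the documents do not support:

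- **That about nine in ten women would lose monitoring.** The 91% applies to one assumed baseline and a borrowed effect size. The real share is unknown.
- **That the 2-hour and the 2 to 6 hour statements contradict each other.** They answer different questions: falling below 450 ms, and returning to baseline.
- **That women are left unobserved or at demonstrated arrhythmic risk.** Scheduled ECGs continue to 8 hours, discharge is restricted, and no arrhythmia is reported at this dose.

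**What to change.** Use one sentence in all three places (5.0 Visit 2, 5.0 Visit 3 and 6.0): continuous ECG monitoring continues until both at least 6 hours have passed since the end of the infusion and the Bazett-corrected QT interval is below 450 ms. Six hours is the upper end of the plan's own return-to-baseline range. If surveillance was already meant to run for the full 8 hours, replace the stop sentence with that statement instead. Leave the scheduled ECGs and the discharge rule unchanged.

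The cost of the 6-hour floor is monitoring time. Forty women with two ibutilide visits each make 80 visits.

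- At most: 80 × 6 = 480 telemetry-hours, if none is now given after the infusion.
- If 2 hours are now given at every visit: 80 × (6 − 2) = 320 added hours.
- If 6 hours or more are already given: none.

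All of this falls inside the 8-hour collection period and the planned stay of about 10 hours. It adds no visit, blood draw or ECG set.
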